Pretreatment: Leucine is commercially available in US as dietary supplements. For this study, we will use oral preparation of the pharmaceutical grade leucine (12 g/day in 2 divided doses for 2 weeks; Ajinomoto, Raleigh, NC) mixed with effervescent powder. PO placebo will resemble the compounded mixture of leucine and effervescent powder. Clinical studies of leucine have used doses ranging from 2 to 18 g/day.⁸¹⁻⁸⁷ According to a meta-analysis, the long-term supplementation dose (i.e., 10 days to 6 months) ranged from 2.8 to 16.1 g/day with a weighted mean of 8.5 g/day.³⁰ Caspenson et al. found that leucine 12 g/day for 2 weeks improved muscle protein synthesis with a concomitant increase in phosphorylation of mechanistic target of rapamycin (mTOR) following the stimulus of a meal.⁸⁷ As this above-average dose given for 2 weeks caused increases in post-prandial protein synthesis and mTOR activation, both mechanisms also observed in preclinical studies of leucine after the stimulus of endotoxin,⁸⁸ we will use 12 g/day for 2 weeks. Participants will be given leucine or PO placebo on the day of in-person screening and will take it for 2 weeks including the morning of endotoxin administration, hence a total of 28 doses. At the end of pretreatment, subjects will indicate the presence or absence of a number of possible adverse effects in a questionnaire using a 4-point scale from 'not at all' to 'very often': symptoms include not feeling well, headache, weakness, fatigue, nausea, vomiting, burping, stomachache, bloating, flatulence, constipation, diarrhea, dry mouth, change of taste, cough, skin complaints, muscle pain, weight gain, weight loss, dizziness, sweating, and shaking. The adherence will be assessed using the Patient Adherence Questionnaire (PAQ)⁸⁹ and the count-back method (i.e., counting doses remaining in returned packets)⁹⁰ at the end of the pretreatment (i.e., immediately before endotoxin).

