Negative Bias in Facial Emotion Recognition (Emotional Face Recognition Task): Depressed subjects have a negative bias in the perception of emotions expressed in faces as they tend to interpret neutral faces as sad and happy faces as neutral.⁷⁶ Furthermore, such a bias appears to play a role in the etiology and maintenance of depression as it predicts relapse in currently depressed and remitted patients.⁷⁷ Emotional Face Recognition Task¹⁰⁴ consists in showing participants a series of black and white photographs (Ekman Pictures of facial affect), in which the facial expression is morphed from neutral to either Sad, Angry, or Happy.¹⁰⁵ For each image, participants will be asked to make a forced choice about the emotion expressed, and rate their certainty on a 0-9 scale. Earlier recognition of a Sad face with certainty would be indicative of negative bias.

For Positive Affect: Subjective Sensitivity to Social Acceptance (Positive Social Feedback Task): Decreased sensitivity to positive social experiences, like social acceptance, is another mechanism that might account for cytokine-induced feelings of social disconnection and depressed mood. The Positive Social Feedback Task was developed based on Izuma et al.'s study involving monetary and social rewards, which demonstrated that positive social feedback robustly activates reward-related brain areas, notably the striatum, and these overlap with the areas activated by monetary rewards.¹⁰⁶ Prior to the experimental session, participants will be asked to complete a survey that contains several personality questionnaires (NEO Five Factor Inventory),¹⁰⁷ as well as several open-ended questions ("What do you do in your free time?" "Briefly describe your personality." "What is your main goal in the future?"). Then, participants will be video-recorded for 2-5 minutes as they discuss what they like about themselves. Participants will be told that 8 people (4 male, 4 female) will form impressions of them—based on their answers to the personality questionnaires and the video-taped self-introduction—by selecting personality traits to describe them. Participants will then see a photograph of themselves along with a descriptive word underneath (supposedly provided by the evaluators), which will be pre-rated based on desirability, and will be asked to rate subjective happiness when each of the feedback items is presented, using a 7-point scale.

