Reward (Reward Learning Task): Anhedonia is a core feature of major depressive disorder and includes a reduction in experienced pleasure (liking reward) and dysfunction in reward anticipation reward learning.⁷⁸⁻⁸⁰ We have found that inflammatory challenge reduces neural sensitivity to reward anticipation.¹⁰⁸ We will use a laboratory based probabilistic reward task that objectively measures participants' ability to modulate behavior as a function of reward, because this task identifies reduced reward learning in depressed patients which is state-dependent and also predicts the persistent diagnosis of depression in the midst of treatment.⁷⁸⁻⁸⁰ This computerized reward-learning task is extensively described in Pizzagalli et al.¹⁰⁹

Order and Timing of Experimental Tasks: The order of the tasks will be first a randomized sequence of Reward Learning and Emotional Face Recognition, then followed by a randomized sequence of Positive Social Feedback and Cyberball Social Exclusion. Because the latter two tasks involve deception, they will be completed only once after the former two tasks, at T₂, time of peak cytokine responses. The former two tasks will be completed at T₀ and T₂.

C.2.7. Interpretation of Results and Potential Pitfalls

As leucine may not inhibit endotoxin-induced inflammation, unopposed sickness symptoms could mask the antidepressant effects of leucine assessed using the POMS. Thus, the results will be statistically adjusted for sickness symptoms. Furthermore, we will use experimental tasks of negative and positive affect to assess mood-specific processes. Although the proposed leucine dose is above average,^{30,87} the adequate antidepressant dose is unknown. Thus, if an interim data analysis for the first 30 participants using 12 g/day shows no signal of an antidepressant effect, we will consider increasing the dose to 16 g/day for the same period of 14 days. Of note, 16 g/day was the maximum dose of leucine used in long-term supplementation studies according to a meta-analysis.³⁰

C.2.8. Statistical Analysis

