The basic design is a 2 group (leucine vs. PO placebo) by 2 condition (endotoxin vs. IV placebo) independent analysis of variance (ANOVA) with one or more repeated outcome measures analyzed with linear mixed models (LMM) with primary focus upon the two endotoxin-exposed groups. The number of repeated measures varies by assessment. The key results are the main effects of pretreatment (i.e., group) while the main effects of group, condition, and their interaction will be tested. For analyses with repeated measures, the two main effects and interaction will further interact with the time variable. POMS will be the primary outcome measure. Simes correction for multiple testing will be applied for the secondary outcome measures as they are expected to be correlated.¹¹⁰

C.2.9. Justification of Sample Size

The effect sizes for the reduction of endotoxin-induced depressive symptoms by leucine within the animal data are very large ($d=.90$), but we have assumed some attenuation in humans ($d=.70$). Assuming an effect of this size, with $n=35$ per group, there is >80% power to detect differences between the leucine and PO placebo pretreatments with endotoxin exposure for the single time point outcomes (e.g., Cyberball Social Exclusion); comparisons for repeated measures assessments will have more power (>90%) and able to detect more subtle effects at >80% power. Both 'leucine + IV placebo' and 'PO placebo + IV placebo' arms are expected to show minimal depression with means over time to be very near zero but exist as reference points to the endotoxin condition, which our previous work suggests to have large effects. With repeated measures, $n=10$ can detect

medium sized effects ($d=.50$) with power $>80\%$. Thus, there is more than adequate power with 35 vs. 10 to show the effect of endotoxin exposure within pretreatment groups.

REFERENCES

3. Depression Guideline Panel: Clinical Practice Guideline 5: Depression in Primary Care, vol 2: Treatment of Major Depression. In: US Department of Health and Human Services PHS, Agency for Health Care Policy and Research, ed. Rockville, MD. 1993.

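### The two Aim 2 tasks done only once have no T0 value and no named baseline covariate; a personality score fixed before the first dose could recover some precision

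*Combined protocol and SAP*

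**What the plan says.** **Tasks.** In C.2.6, Order and Timing of Experimental Tasks, the Reward Learning and Emotional Face Recognition tasks have a pre-endotoxin value: "The former two tasks will be completed at T₀ and T₂". Positive Social Feedback and Cyberball do not: "Because the latter two tasks involve deception, they will be completed only once after the former two tasks", and that single occasion is T2.

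**Personality survey.** C.2.6 states that, at some point before the experimental session, "participants will be asked to complete a survey that contains several personality questionnaires (NEO Five Factor Inventory". The one role it describes is that supposed evaluators form impressions of the participant "based on their answers to the personality questionnaires and the video-taped self-introduction". The inventory is absent from the baseline measures and the moderators listed in C.2.4, and from C.2.8.

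**Start of study drug.** C.2.3, Pretreatment: "Participants will be given leucine or PO placebo on the day of in-person screening and will take it for 2 weeks".

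**Analysis.** C.2.8: "The basic design is a 2 group (leucine vs. PO placebo) by 2 condition (endotoxin vs. IV placebo) independent analysis of variance (ANOVA". The terms named are group, condition, their interaction and, for repeated measures, time. No baseline covariate is named. C.2.7 announces an adjustment for sickness symptoms while discussing the POMS, then presents the affect tasks as a further safeguard.

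**Power.** C.2.9 assumes d = .70 with 35 per group and claims more than 80% "power to detect differences between the leucine and PO placebo pretreatments with endotoxin exposure for the single time point outcomes", naming Cyberball as the example. It claims more than 90% for repeated measures.

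**The concern.** An outcome measured before and after endotoxin can use its own earlier value to remove stable differences between people. These two tasks cannot, so lasting differences in how strongly people react to exclusion or praise stay in the error term. A trait measure that plausibly relates to both reactions is already being collected, yet the plan gives it no place in the analysis.

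C.2.9 itself treats single-time-point outcomes as the less well powered group. The tasks also matter for interpretation, because the plan relies on them to separate mood effects from sickness. A covariate named in advance and measured before the first dose would leave the randomised comparison unbiased. It would narrow the interval to the extent that it predicts the outcome. Naming it in advance also closes off choosing covariates after unblinding.

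**Working it through.** **Inputs.** From C.2.9: d = .70 (SD = 1) and n = 35 per endotoxin arm. Assumed because the documents do not state them: two-sided alpha of 0.05, and r, the within-arm (multiple) correlation between covariates and outcome, shown from 0 to .5.

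**Step 1: reproduce the plan's figure.** The noncentrality parameter is d / sqrt(2/n) = 0.70 / sqrt(2/35) = 0.70 / 0.239 = 2.928. With 68 degrees of freedom the critical t is 1.995 and power is 82.3%. A normal approximation gives 83.4%, and the four-arm error degrees of freedom (90 − 4 = 86) give 82.5%. The claim of more than 80% holds.

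**Step 2: add a covariate.** The residual SD is multiplied by sqrt(1 − r²), so the noncentrality parameter becomes 2.928 / sqrt(1 − r²). One degree of freedom is lost (67 remain). The equivalent sample size without a covariate is 35 / (1 − r²) per arm. The 95% half-width is t × sqrt(2/35) × sqrt(1 − r²), in SD units.

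| r | sqrt(1 − r²) | Power | 95% half-width | Equivalent n per arm |
|---|---|---|---|---|
| 0 (no covariate) | 1.000 | 82.3% | 0.477 | 35.0 |
| .1 | 0.995 | 82.7% | 0.475 | 35.4 |
| .2 | 0.980 | 83.8% | 0.467 | 36.5 |
| .3 | 0.954 | 85.7% | 0.455 | 38.5 |
| .4 | 0.917 | 88.3% | 0.437 | 41.7 |
| .5 | 0.866 | 91.5% | 0.413 | 46.7 |

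A second covariate (66 degrees of freedom) lowers each power by less than 0.05 points at the same r.

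**Step 3: how far to trust the table.** It ignores chance imbalance in the covariate, which for one normally distributed covariate inflates the variance on average by 1 + 1/(2n − 4) = 1 + 1/66 = 1.015. At r = .1 the net variance factor is 0.99 × 1.015 = 1.005, so there is no gain. At r = .3 it is 0.91 × 1.015 = 0.924, so most of the gain remains. The table is therefore slightly favourable to adjustment.

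**Step 4: is the score a baseline score?** C.2.6 fixes the survey only as before the experimental session. C.2.3 starts study drug on the screening day, two weeks before that session. A survey completed at any point in those two weeks would satisfy C.2.6 and still follow the first dose. As written, a pre-dose score is possible but not assured.

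**The case against.** **The gain is unproven.** No part of the documents gives r or says that the inventory predicts either outcome. The larger gains need r of .4 or .5, which nothing in the documents supports. This stands, and it limits the conclusion to a possible loss of precision.

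**Positive Social Feedback may not yield a single number.** Happiness is rated for each feedback item, and the words are graded for desirability beforehand. If the analysis contrasted items within a person, it could remove stable rating tendencies without a covariate. The plan does not say how the items are scored. This also stands: the table applies to a single summary score per person.

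**The screening visit is already full.** The Lay Summary allows 90 minutes, and C.2.2 and C.2.4 fill it with interviews, mood, anxiety and sleep scales and a cognitive battery. Adding the inventory is a small but real burden.

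**Stronger readings that the documents do not support:**
- *The inventory is only a cover story.* One use is described and none is excluded. The accurate statement is that no analysis use is stated.
- *The tasks are compared without any adjustment.* C.2.7's sickness adjustment might extend to them; its scope is unclear. It would not answer the point, since sickness after endotoxin is not a baseline covariate.
- *Simes correction cuts power to 64.2%.* That figure follows from a threshold of 0.05/4 = 0.0125, the strictest Simes step for a family of four outcomes. The plan does not define such a family, and the other Simes steps are less strict.
- *The trial already holds this precision.* Step 4 shows that a pre-dose score is not assured.

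**Conclusion.** The point holds as a modest efficiency gain on two secondary outcomes. Both tasks lack a T0 value, no baseline covariate is named for them, and an inventory that could supply one has no stated analysis use and no guaranteed pre-dose timing.

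On the plan's own d and sample size, with two-sided 0.05 assumed, adjustment would raise power from 82.3% to between about 84% and 92% for r from .2 to .5. At r of .1 or less it would do essentially nothing. The size rests on r, which is an assumption, and on one summary score per task.

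A reader might infer that the comparisons are biased or that the power statement is wrong. Neither follows: randomisation protects the comparison without covariates, and the figure of more than 80% reproduces. The primary outcome, the POMS, is unaffected.

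**What to change.** - **C.2.6:** have the NEO Five Factor Inventory completed at the in-person screening visit, before the first dose. The answers would still precede the session, so the task's cover story is unchanged.
- **C.2.8:** pre-specify neuroticism as covariate for Cyberball distress, and neuroticism and extraversion for Positive Social Feedback happiness. Keep the comparison without these covariates as a sensitivity analysis. State how the Positive Social Feedback items are combined.
- **If the inventory cannot precede dosing:** use an anxiety or depression scale from the C.2.4 screening measures. Excluding people with PHQ-9 of 5 or more probably narrows the range of such scales and lowers the gain.

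**Cost:** about two sentences of text, a slightly longer screening visit, and one or two of 68 degrees of freedom. If the covariates prove unrelated to the outcome, the expected variance penalty is about 1.5% for one covariate (1/66) and 3% for two (2/65). No new instrument, visit or participant is needed.

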B.2. A novel pharmacologic agent shown to act on a novel mood mechanism in animal model

Leucine has been shown to abrogate endotoxin-induced depression-like behavior in mice by specifically acting on blood-to-brain transport of excessively produced KYN without affecting inflammatory responses (Preliminary Data). Although leucine has been studied in humans for other purposes, it has never been tested for depression. This study will employ this novel paradigm for the first time in humans.

B.3. Task based multi-dimensional methods to evaluate affective processes

No prior experimental research on inflammation and depression has used innovative objective measures to assess negative and positive affective processes. Given that social disconnection plays a critical role in the

onset and perpetuation of depression,^{58,74} we will examine distress following an experimental episode of social rejection as a function of pretreatment conditions. Further, we will examine the impact of pretreatments on accurate judgment of facial emotions with implications for perceived threat (i.e., angry face) or reward value (i.e., happy face).⁷⁵ Facial emotion recognition task is used to identify negatively biased processing of emotional faces and is associated with depression and risk of relapse in depressed patients.^{76,77} This study is novel also by evaluating positive affective responses, using reward-based tasks.⁷⁸⁻⁸⁰ Use of these experimental affect tasks is strategic in distinguishing the effects of endotoxin on depressive symptoms from its effects on sickness symptoms. Furthermore, understanding how leucine pretreatment influences negative and positive affect in response to endotoxin has the potential to refine pharmacologic strategies of depression treatment and to inform the design of neuroimaging studies aimed at identifying the neural sensitivities related to inflammation. For example, findings related to reward deficits could direct attention toward pharmacologically targeting neurotransmitters (i.e., dopamine) and toward scanning reward-related brain regions.

C. APPROACH

C.1. Preliminary Studies

C.1.1. Leucine abrogates inflammation-induced depression-like behavior

Aim: We examined whether L-leucine (hereafter referred to as leucine), which has a high affinity for LAT1, competitively inhibits KYN binding to LAT1, reduces blood-to-brain KYN transport, and blocks endotoxin-induced depression-like behavior in mice.

[figure not shown]

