Behavioral Measures: Depressed mood, a core symptom of depression, will be assessed immediately before endotoxin administration (T_0) and then hourly for the next 6 hours (T_1-T_6) using the POMS⁶⁷ (primary outcome). We will also use the MADRS⁹⁷ hourly (T_0-T_6) as it is sensitive to acute changes in depressed mood and anhedonia following endotoxin¹⁹ and is less oriented towards somatic symptoms than the Hamilton Depression Rating Scale. Because feelings of social disconnection and loneliness predict depression and co-occur with depressed mood following inflammatory challenge, feelings of social disconnection (Feelings of Social Disconnection Scale²¹) and loneliness (adapted UCLA Loneliness Scale⁹⁸) will also be assessed.

Participants will also complete self-report measures of sickness symptoms (e.g., muscle pain, fatigue).

Cognitive Measures: Three items from the POMS-Confusion subscale (unable to concentrate, forgetful, confused) will be assessed at T_0 and then hourly (T_1-T_6).⁶⁷ Verbal memory, visual memory, executive function, and attention be assessed at T_0 and then between T_2 and T_3 using computerized tests from CNS Vital Signs™: Verbal Memory Test, Visual Memory Test, Stroop Test, Shifting Attention Test, and Continuous Performance Test. Reichenberg et al. assessed cognitive impairment at 1, 3, and 9 hours after endotoxin and found it to be worst at 3 hours.²⁰ The order of tests will be counterbalanced across subjects to avoid any non-random version-dependent bias.⁹⁹

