Cytokines, Kynurenone Metabolites & Gene Expression Analysis: Blood samples will be collected immediately before endotoxin administration (T_0) and then hourly (T_1-T_6). Samples will then be appropriately processed and stored for later assessment of proinflammatory cytokines (IL-1 receptor antagonist, IL-6, TNF- α , soluble TNF receptor) and KYN metabolites (TRP, KYN, 3HK, QA, KynA). Depressed mood and biomarkers will be hourly assessed even after the time of peak responses (T_2) because depressed mood can linger and has been shown to correlate with cytokines and kynurenone metabolites.^{16,42} At baseline prior to pretreatment, immediately before endotoxin injection (T_0), and 30 minutes post-injection ($T_{0.5}$), blood samples will be drawn in PaxGene RNA tubes, which preserve RNA integrity. Genome-wide transcriptional profiling will be conducted using Illumina HT-12 BeadArrays. Gene expression analysis will provide information on the underlying biological mechanisms of inflammatory and affective responses, and in particular, will be used to independently replicate the findings of our prior endotoxin studies.

C.2.6. Experimental Tasks (Main Study Session)

For Negative Affect: **Subjective Sensitivity to Social Rejection (Cyberball Social Exclusion Task):** Feelings of 'social disconnection' play a critical role in the onset and perpetuation of (non-inflammatory forms of) depression.¹⁰⁰ Inflammatory processes can trigger social withdrawal¹⁰¹ and increase feelings of distress and related neural sensitivity (i.e., activation of the dorsal anterior cingulate cortex).²¹ Using the Cyberball Social Exclusion Task,¹⁰² we will examine feelings of social distress. Participants will be told that they will play a virtual ball-tossing game with two other players over the Internet. In reality, they will play with a preset computer program. In the first round (inclusion), participants will play with the two other players for the entire period. In the second round (exclusion), participants will receive the ball for 7 throws and then will be excluded for the rest of the round when the two players will stop throwing the ball to the participant. Following this task, they will complete a measure of social distress in response to social exclusion.¹⁰³

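### Two emotion-provoking social tasks run at T2, in random order, inside the hourly POMS/MADRS series; the T2 ratings are not placed before them and task order is not in the model

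*Combined protocol and SAP*

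**What the plan says.** All references are to the combined protocol and SAP.

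- **Primary outcome schedule (C.2.5, Behavioral Measures).** POMS depressed mood is rated just before the injection (T0) "and then hourly for the next 6 hours", which gives six post-challenge values, T1 to T6. MADRS follows the same hours. C.2.5 explains why ratings go on past T2: "Depressed mood and biomarkers will be hourly assessed even after the time of peak responses", because low mood can persist.
- **Social tasks (C.2.6).** Reward Learning and Emotional Face Recognition come first, "then followed by a randomized sequence of Positive Social Feedback and Cyberball Social Exclusion". Of the last two, C.2.6 says "they will be completed only once after the former two tasks, at T₂, time of peak cytokine responses".
- **What those tasks provoke.** After Cyberball, participants are excluded and "they will complete a measure of social distress in response to social exclusion". In Positive Social Feedback they "will be asked to rate subjective happiness when each of the feedback items is presented, using a 7-point scale".
- **Aim 2 (Specific Aims; B.3).** Responses to rejection and acceptance are expected to differ by pretreatment. B.3 puts it as "we will examine distress following an experimental episode of social rejection as a function of pretreatment conditions".
- **Model (C.2.8).** A linear mixed model has pretreatment group, challenge condition, their interaction, and the interactions of these with time. C.2.7 adds an adjustment for sickness symptoms. There is no term for the tasks or their order.
- **Saline arms (C.2.9).** The two arms of 10 are "expected to show minimal depression with means over time to be very near zero".

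The T0 rating is tied to the injection. The T2 rating is not tied to the tasks in either direction, and the time of debriefing is not given.

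**The concern.** Aim 1 is about mood caused by endotoxin. From T2 onward each participant has also been excluded from a game and given social feedback, both chosen because they move emotion. A later POMS value may therefore hold two components, and the plan gives no direct way to tell them apart.

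Three things are at stake:

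- **Meaning of the primary contrast.** If leucine alters how strongly people react to rejection or praise, part of a POMS difference after T2 could come from that reaction, yet it would be reported under Aim 1.
- **Independence of the evidence.** A.6 and C.2.7 offer the tasks as mood-specific evidence beyond POMS. If task reactions carry into POMS, the two are less independent than they appear.
- **Precision of the task scores.** The second social task follows whatever mood shift the first produced. The order is known for everyone but is left in the error term.

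**Working it through.** **Inputs from the documents.** n = 35 per endotoxin arm, 10 per saline arm, d = .70, power above 80% for a single time point and above 90% for repeated measures (C.2.9). **Assumed, because not stated:** two-sided alpha 0.05, within-person correlation rho, size of the order effect, and duration of task mood.

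**1. The plan's own figure.** Two-sample noncentral t, 68 df, noncentrality .70 × √(35/2) = 2.93: power 82%. The claim of more than 80% is reproduced.

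**2. How many POMS values follow the tasks.** T3 to T6: 4/6 = 67%. With T2: 5/6 = 83%. This counts timing only; it does not show that task mood is present.

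**3. How much task mood could remain.** Take a reaction at T2 with half-life h, so that the share left after t hours is 0.5^(t/h). The mean over T1-T6 is the sum over T3-T6 divided by 6. The last column assumes that leucine changes task reactivity by 0.3 SD and has no effect on endotoxin mood.

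| Assumed half-life | Left at T3 | Left at T6 | Mean over T1-T6 | Leucine contrast on mean POMS |
|---|---|---|---|---|
| 0.25 h | 6% | <0.1% | 1% | 0.003 SD |
| 0.5 h | 25% | 0.4% | 6% | 0.02 SD |
| 1 h | 50% | 6% | 16% | 0.05 SD |
| 2 h | 71% | 25% | 30% | 0.09 SD |
| no decay | 100% | 100% | 67% | 0.20 SD |

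If the T2 rating also follows the tasks, the no-decay figure is 0.3 × 5/6 = 0.25 SD. The 0.20-0.25 SD figures are upper cases for a 0.3 SD reactivity effect.

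**4. Can the saline arms separate the two sources?** For one time point, in SD units, the standard error of leucine vs placebo is √(2/10) = 0.45 under saline and √(2/35) = 0.24 under endotoxin. For the interaction it is √(0.200 + 0.057) = 0.51. A reactivity effect of 0.3 SD is smaller than the saline standard error.

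**5. Cost of omitting order, single-time-point task scores.** A 50:50 order effect of e residual SDs adds variance e²/4, so the effective d is .70/√(1 + e²/4). The between-arm difference in order share has SD √(2 × 0.25/35) = 0.12 under simple randomisation.

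| e (assumed) | Added variance | Chance imbalance (SD) | Power |
|---|---|---|---|
| 0 | 0 | 0 | 82% |
| 0.25 | 1.6% | 0.03 | 82% |
| 0.5 | 6% | 0.06 | 80% |
| 0.75 | 14% | 0.09 | 77% |
| 1.0 | 25% | 0.12 | 73% |

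**6. Cost of omitting order, mean POMS over T1-T6.** Under compound symmetry the variance of the mean is (1 + 5 rho)/6. At rho 0.7 it is 0.75, so d = .70/√0.75 = 0.81 and power is 91.5%. An order effect e carried undiminished over T3-T6 adds (4e/6)²/4.

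- e = 0.5, no decay: adds 0.028, power 90.5%. With a 1 h half-life: 91.5%.
- e = 0.5, no decay, T2 also affected: adds (5 × 0.5/6)²/4 = 0.043, power 90.0%.
- e = 1.0: 87.5% with no decay, 91.3% with a 1 h half-life.
- At rho 0.5, e = 0.5, no decay: from 96.6% to 95.8%.

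**7. Power of a pre-task analysis.** With T1 and T2 only, the variance of the mean is (1 + rho)/2. Power is 92%, 88% and 86% at rho 0.5, 0.7 and 0.8. With all six values it is 97%, 92% and 89%. These figures assume d = .70 at T1 as well as at T2.

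**The case against.** Several stronger readings are tempting, and the documents do not support them.

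- **A reader might infer that most POMS values do mix the two sources of mood.** The count shows only that they come later. Mixing across T3-T6 needs task mood to last one to four hours, and no duration is given. With fast decay mainly T3 is touched, and T2 if it is rated afterwards.
- **A reader might infer that the leucine comparison is biased.** No arm is exempted from the tasks, so an additive task effect cancels between randomised arms. Order is randomised too, so it brings noise and chance imbalance rather than systematic bias.
- **A reader might infer that power for the primary outcome falls to 73%.** That figure belongs to single-time-point scores such as Cyberball. Step 6 shows a far smaller loss for averaged POMS.

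The authors could add that Aim 2 itself treats responses to rejection and acceptance as responses to endotoxin. If endotoxin heightens reactivity and leucine dampens it, that is arguably part of the effect of interest; only a leucine effect on reactivity apart from endotoxin would clearly mislead. The group-by-condition-by-time terms bear on this, T1 is always free of the social tasks, and a difference appearing only after T2 would be visible.

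Most of this stands, and it limits the point. It does not remove it. Mood elicited by a laboratory exclusion is not the same quantity as spontaneous mood after endotoxin, even if both are inflammation-dependent. The interaction rests on 10 per saline arm (step 4). And C.2.8 makes the pretreatment main effect the key result, so a late-appearing difference would be noticed only on secondary inspection.

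**Conclusion.** The point holds in limited form and should be addressed. Four of six post-challenge POMS values, or five if the T2 rating comes after the tasks, may carry task-induced mood. If pretreatment changes task reactivity, a POMS difference after T2 cannot be cleanly assigned to Aim 1, and the saline arms and planned interactions separate the two only weakly. The size is unknown: for an assumed 0.3 SD effect on reactivity it runs from almost nothing to 0.20-0.25 SD on mean POMS, depending wholly on how long task mood lasts.

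Omitting order is a matter of precision. It matters for the two task scores (82% to 73% at the top of the assumed range) and hardly for averaged POMS: about one point or less for a 0.5 SD order effect over T3-T6, and 1.5 points if T2 is also affected with no decay. The order effects, half-lives, rho and alpha are assumptions.

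The most concrete gap is the unstated sequence at T2. That is the hour of peak cytokine response, and its rating is spared or exposed according to which comes first.

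**What to change.** - **C.2.6:** state that the T2 POMS and MADRS are completed before any T2 task begins.
- **C.2.8, task scores:** include randomised task order (exclusion last vs feedback last) as a covariate for the Cyberball and Positive Social Feedback scores. Optionally, add order and its interaction with the post-T2 hours to the POMS and MADRS models.
- **C.2.8, sensitivity analysis:** pre-specify one analysis of the pretreatment contrast on T0-T2 only. With the T2 rating placed first, this answers Aim 1 free of the social tasks. It should be fixed before unblinding, since chosen later it would look data-driven.

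**Cost:** one sentence in the session procedure, a few model degrees of freedom, and no new data. The sensitivity analysis has less power than the full series (about 86-92% at assumed rho 0.8-0.5, against 89-97%), so it should support the primary analysis rather than replace it.
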